9.4.3. Considerations for Patients with Co-morbid Conditions

9.4.3.1. Patients with Type 2 Diabetes Mellitus

In Part A of the study, all patients with type 2 diabetes mellitus are excluded. In addition, in both Part A and Part B, patients with type 1 diabetes mellitus are excluded.

Patients with type 2 diabetes mellitus are permitted in Part B of the study if their disease is controlled, with hemoglobin A1c \leq 7% at screening. Such patients should receive appropriate diabetes management during the study, with treatment as deemed appropriate, with the goal of maintaining stable disease with hemoglobin A1c \leq 7% throughout the trial.

Gestational diabetes and steroid induced diabetes occurring in the past and resolved prior to screening are not exclusionary.

The treating investigator should ensure that diabetic patients that are included in the study are closely monitored for signs or symptoms of macular edema. (See [Section 12.4](#)) Patients with diabetic uveitis or retinopathy or other co-morbid conditions due to their diabetes are excluded.

Duration of disease and medication history for 3 months prior to randomization and throughout the study will be recorded in source documents and in the eCRF.

9.4.3.2. Patients with History of Cardiac Disease

In Part A of the study, patients with any clinically relevant cardiovascular conditions, as listed out in the exclusion criteria ([Section 9.4.2](#)), are excluded from participating in the study.

In Part B, patients with some pre-existing cardiac conditions, who have stable disease and would not be placed at significant safety risk by participating in the study, may be considered for participation in Part B of the study. Please refer to [Section 9.4.2](#) for a list of cardiac exclusion criteria for Part B. These patients should have a cardiology consultation to determine whether it is appropriate for them to participate in Part B of the study and whether they need additional

cardiac monitoring, such as being monitored for an extended period of time and/or possible extended continuous ECG monitoring overnight in a medical facility.

If more intensive monitoring is not deemed necessary by the consulting cardiologist, these patients will follow the detailed first dose monitoring procedures as outlined in [Section 10.2.1.1](#). The treating investigator should ensure these patients included in the study are closely monitored for signs of any bradycardia or other rhythm disturbances after the first dose of RPC1063, as these patients may be at higher risk for cardiac adverse events.

9.4.4. Withdrawal of Patients from Study Medication and/or the Study

9.4.4.1. Discontinuation of Study Medication

Reasons for discontinuation include, but are not limited to the following:

- Investigator decision

The Treating Investigator may discontinue study medication if it is determined that it is not safe or in the patient's best interest to receive further treatment. The Medical Monitor should be promptly notified of the decision.

- Noncompliance: after consultation between the investigator, the Medical Monitor, or Study Monitor, and the sponsor when appropriate, a patient may be discontinued from study medication for failure to comply with protocol requirements
- Intercurrent illness: A patient may be discontinued from study medication if, in the judgment of the treating investigator, the patient develops an intercurrent illness or complication that is not consistent with the protocol requirements or that, in any way, justifies discontinuation of study medication.
- Protocol-defined adverse events of special interest (see [Section 12.4](#)):
 - Confirmed AST or ALT >5 times the upper limit of the normal range, confirmed upon retest within 14 days of the original lab value (unless determined by the investigator to not be of hepatic origin)
 - A diagnosis of macular edema, which is new or worsening since baseline
 - FEV1 or FVC <50% of predicted values
- If the patient becomes pregnant
- Sponsor termination or suspension of the study

All patients who discontinue study medication should complete an Early Termination Visit (see [Table 2 \[Part A\]](#) and [Table 4 \[Part B\]](#)). Unless the patient withdraws consent or is lost to follow-up, they will be asked to undergo a follow-up visit 4 weeks after the last dose for the collection of safety data including lymphocyte recovery and to assess their disease status. Alternative treatment for multiple sclerosis (with the exception of medication given in the context of another clinical trial) can be started, if needed, after the early termination visit.

The reason for discontinuation of study medication will be recorded in the clinical records and the patient's eCRF.

9.4.4.2. Withdrawal of Patients From the Study

Patients must be withdrawn from the study for any one of the following reasons:

- The patient is lost to follow up (i.e., those patients whose status is unclear because they fail to appear for study visits without stating an intention to withdraw), the investigator should show due diligence by documenting in the source documents steps taken to contact the patient (e.g., dates of telephone calls, registered letters).
- Patient withdrawal of consent. Every effort should be made within the bounds of safety and patient choice to have each patient complete the study. If a patient withdraws consent, the only additional study data to be collected will be the follow up of SAEs as mandated by the protocol.

The reason for the patient's withdrawal from the study must be recorded in the clinical records and the patient's eCRF.

9.5. Treatment

9.5.1. Treatments Administered

The Investigator must ensure that the investigational product will be used only in accordance with the protocol.

Part A of the study is randomized and double-blinded with regard to treatment with RPC1063 and matching placebo in order to prevent bias in treatment allocation and in the assessment of effect. The Investigator site personnel, as well as the Sponsor and their representatives involved in the monitoring or conducting the study, and the patients will all be blinded to the study drug codes.

Part B of the study is randomized and double-blind, double-dummy with regards to treatment with RPC1063 or IFN β -1a and their corresponding matching placebo in order to prevent bias in treatment allocation and in the assessment of effect. The prolonged treatment period (24 months) will provide additional safety and efficacy data; information that is relevant to RMS, a chronic, highly variable, slowly progressing disease.

In both Part A and Part B of the study, a "dual assessor" approach will be used to evaluate efficacy and safety to prevent potential unblinding as result of observed efficacy, AEs, or laboratory changes

Part A

In Part A, patients will be randomly assigned 1:1:1 on Day 1 to one of following 3 treatment regimens:

- Placebo oral capsule daily for 24 weeks
- 0.5 mg RPC1063 oral capsule daily for 24 weeks
- 1 mg RPC1063 oral capsule daily for 24 weeks

For all patients in Part A, initial study treatment will consist of a 7-day dose titration regimen as follows (see Table 6): for patients randomized to receive active treatment with RPC1063, this regimen will consist of 0.25 mg RPC1063 starting on Day 1 for 4 days and 0.5 mg RPC1063

starting on Day 5 for 3 days. All patients will be dosed with their assigned treatment level beginning on Day 8.

Table 6 Titration Schedule for the RPC1063 Treatment Groups in Part A

Assigned treatment	RPC1063/Placebo dose (# capsules)		
	Days 1 to 4	Days 5 to 7	From Day 8 on
RPC1063 0.5 mg	0.25 mg (1 x 0.25 mg capsule)	0.5 mg (2 x 0.25 mg capsules)	0.5 mg (1 x 0.5 mg capsule)
RPC1063 1 mg	0.25 mg (1 x 0.25 mg capsule)	0.5 mg (2 x 0.25 mg capsules)	1 mg (1 x 1 mg capsule)
Placebo	Placebo (1 capsule)	Placebo (2 capsules)	Placebo (1 capsule)

Study medication will begin following randomization ([Section 13.4](#)) on Day 1. Patients will take capsule(s) daily through Week 24.

Capsule dosing: dosing will be once daily in the morning in fasting conditions (before breakfast).

On days of study visits on which a pre-dose PK sample will be obtained (Day 1 and Week 12 in Part A, Day 1 and Month 12 in Part B), patients should be instructed to withhold the dose and their morning meal until the office visit, and dose will be administered during the visit.

Part A Blinded Extension Period

In the blinded extension period of Part A, patients will receive 1 of the 2 following treatment regimens:

- 0.5 mg RPC1063 oral capsule daily beginning on Week 25
- 1 mg RPC1063 oral capsule daily beginning on Week 25

RPC1063 0.5 mg or 1 mg patients who have completed the 24-week placebo-controlled treatment period and who choose to participate in the blinded extension period will continue in their respective treatment groups.

Placebo patients who have completed the 24-week placebo-controlled treatment period and who choose to participate in the blinded extension period will be randomized 1:1 to either the 0.5 mg or 1 mg RPC1063 treatment regimen.

All patients who participate in the optional blinded extension period will have an initial 7-day dose titration period as shown in [Table 6](#): 0.25 mg RPC1063 starting on Day 1 for 4 days and 0.5 mg RPC1063 starting on Day 5 for 3 days. Day 1 cardiac monitoring procedures will also be performed on the first day of dose titration, as shown in [Table 5](#). (Holter monitoring will not be included in these cardiac monitoring procedures.) Patients will be dosed with their assigned treatment level beginning on Day 8.

Patients who opt to enter the optional, blinded extension period will continue to receive study drug until all patients who choose to participate have received at least 48 weeks of treatment (total of at least 72 weeks, 24 weeks in the placebo-controlled period and at least 48 weeks in the blinded extension).

Treatment in case of relapse is described in [Section 9.1.2.3](#).

Part B

In Part B, patients will be randomized 1:1:1 to receive one of the following 3 regimens:

- IFN β -1a 30 μ g IM injection weekly for 24 months
- 0.5 mg RPC1063 oral capsule daily for 24 months
- 1 mg RPC1063 oral capsule daily for 24 months

Dosing will begin following randomization on Day 1.

Part B will be use a double-dummy design. Thus, patients randomized to RPC1063 0.5 or 1 mg will also receive weekly matching placebo IM injections and patients randomized to IFN β -1a 30 μ g will also receive daily matching placebo oral capsules.

For all patients in Part B, initial study treatment will consist of a 7-day dose titration regimen as shown in [Table 7](#): for patients randomized to receive treatment with RPC1063, this regimen will consist of 0.25 mg RPC1063 starting on Day 1 for 4 days, and 0.5 mg RPC1063 starting on Day 5 for 3 days. All patients will be dosed with their assigned RPC1063 treatment level beginning on Day 8. Patients randomized to IFN β -1a 30 μ g will receive RPC1063-matching placebo titration kits.

Table 7 Titration Schedule for the RPC1063 Treatment Groups in Part B

Assigned treatment	RPC1063/IFN β -1a dose (# RPC1063/Placebo capsules)			
	Day 1	Days 2 to 4	Days 5 to 7	Day 8*
RPC1063 0.5 mg	0.25 mg RPC1063 (1 x 0.25 mg capsule) + Placebo IM injection	0.25 mg RPC1063 (1 x 0.25 mg capsule)	0.5 mg RPC1063 (2 x 0.25 mg capsules)	0.5 mg RPC1063 (1 x 0.5 capsule) + Placebo IM injection
RPC1063 1 mg	0.25 mg RPC1063 (1 x 0.25 mg capsule) + Placebo IM injection	0.25 mg RPC1063 (1 x 0.25 mg capsule)	0.5 mg RPC1063 (2 x 0.25 mg capsules)	1 mg RPC1063 (1 x 1 mg capsule) + Placebo IM injection
IFN β -1a 30 μ g	IFN β -1a 30 μ g- IM injection + Placebo (1 capsule)	Placebo (1 capsule)	Placebo (2 capsules)	IFN β -1a 30 μ g- IM injection + Placebo (1 capsule)

* From Day 8 on, patients will continue receiving weekly IM injections (IFN β -1a/ placebo) and daily capsules (RPC1063/placebo) according to the assigned treatment level

IFN β -1a 30 μ g (and matching placebo) will be supplied in sealed plastic trays containing one prefilled syringe for IM injection for each dosing interval. Patients will be instructed by a nurse or physician how to self-administer injections. The first injection will be self-administered under the supervision of a nurse or physician. Thereafter, patients will self-administer their study treatment (IFN β -1a or matching placebo) once weekly. Further instructions on how patients

CONFIDENTIAL

The information contained herein may not be used, disclosed, or published without the written consent of Receptos.

should self-inject are provided in the study injection guide (information for the user) that will be provided to the patients.

RPC1063 and matching placebo capsules will be taken in fasting conditions as described above in Part A.

Treatment in case of relapse is described in [Section 9.1.2.3](#).

On the days of IFN β -1a/placebo IM injection administration, prophylactic treatment of flu-like symptoms is recommended as follows:

- Acetaminophen (paracetamol) or ibuprofen within 1 hour prior to each IFN β -1a injection, and then approximately every 6 hours for the 24 hours following each injection.

If the patient cannot take either acetaminophen (paracetamol) or ibuprofen, then the patient may take:

- Naproxen within 1 hour prior to IFN β -1a injection, and then approximately every 12 hours for the 24 hours following each injection.

If the patient cannot take acetaminophen (paracetamol), ibuprofen, or naproxen, then:

- Aspirin may be administered within 1 hour prior to each IFN β -1a injection and then approximately every 4 to 6 hours for the 24 hours following each injection.

Patients may take additional doses of acetaminophen (paracetamol), ibuprofen, naproxen, or aspirin within a 24-hour period as necessary for the relief of IFN-related flu-like symptoms.

Patients should be told to refer to the medication label/packaging for the recommended individual and maximum total doses within any 24-hour period.

Instructions for Missed Dose(s) of RPC1063/Placebo Capsules

Patients should be instructed that if they forget to take a dose, they can take the dose within 4 hours of the normal dosing time; otherwise they should take their next dose at the regular time on the following day. If the patient vomits the capsule, he/she should be instructed not to take another capsule on the same day, but to take the next dose at the regular time on the following day. If the patient is ill and unable to take a dose, 2 days without treatment is acceptable, otherwise the patient will contact the Investigator.

If a patient misses a dose during dose titration, the Medical Monitor should be contacted to discuss completing the dose titration schedule.

If the patient misses more than 7 consecutive doses for any reason, Day 1 cardiac monitoring procedures will be performed on the first day that the patient resumes dosing (Holter monitoring will not be performed). If a patient misses more than 14 consecutive doses for any reason, the Medical Monitor must be contacted to discuss procedures for resuming therapy, which may include an additional dose titration schedule if deemed appropriate.

Instructions for Missed Dose of IFN β -1a/Placebo Injection

Patients should be instructed that if they forget to take a dose, they can administer the injection within 2 days of the scheduled weekly dosing day. Prophylactic treatment should be administered prior to injection as described above. If the patient does not administer the

injection within 2 days of the scheduled injection day, they should take their next dose on the next scheduled weekly injection day.

9.5.2. Study Treatment Formulation

RPC1063 Capsules and Placebo

The drug substance will be manufactured, quality control checked and released in accordance with good manufacturing practices at [REDACTED] will supply the study medication (RPC1063 capsules and matching placebo).

RPC1063 and placebo will be provided as powder-filled capsules. RPC1063 drug substance is blended with [REDACTED]

capsules. Three RPC1063 dosage strengths have been prepared for the clinical investigations; 0.25 mg ([REDACTED] capsule), 0.50 mg ([REDACTED] capsule), and 1.0 mg ([REDACTED] capsule).

For placebo, the same [REDACTED] capsules will contain the same blended excipients described above. All three doses of RPC1063 and placebo capsules are identical in appearance.

The capsules will be orally administered singularly, or in varying combinations, to achieve the desired dose for clinical studies.

IFN β -1a and Matching Placebo

IFN β -1a is commercially available and is manufactured by [REDACTED]. Stocks of IFN β -1a will be purchased directly from the supplier and supplied by [REDACTED]

IFN β -1a matching placebo will be manufactured, quality control checked and released in accordance with good manufacturing practices at [REDACTED]. IFN β -1a matching placebo for injection will contain 0.9% Sodium Chloride.

Study treatment IFN β -1a and matching placebo will be supplied in prefilled syringes, which will be dispensed to patients at each visit and will contain a sufficient supply of IFN β -1a 30 μ g/0.5 mL for IM injection at each dosing interval.

Study treatment (IFN β -1a or matching placebo) prefilled syringes and needles are for one-time use only; any study treatment remaining should not be used for another dose.

All study medication must only be dispensed by a Pharmacist or medically qualified staff and is to be dispensed only to patients enrolled in this study.

9.5.3. Study Treatment Labeling and Packaging

RPC1063 capsules will be packaged in [REDACTED] (35 capsules per bottle, apart from the titration kits), closed with a [REDACTED] child resistant screw-cap that is induction sealed.

The labeling will be in accordance with GCP and any other local regulatory requirements.

Details unique to Parts A and B are described below.

Part A

CONFIDENTIAL

The information contained herein may not be used, disclosed, or published without the written consent of Receptos.

Similar to RPC1063 capsules, placebo capsules will be packaged in [REDACTED] (35 capsules per bottle for treatment medication capsules, and 12 capsules per bottle in the titration kits), closed with a [REDACTED] child resistant screw-cap that is induction sealed. The cap on the treatment bottles will be white, and the cap on the titration bottles will be blue.

The labeling will be in accordance with GCP and any other local regulatory requirements.

Part B

IFN β -1a and matching placebo injections will be supplied in prefilled syringes, which will be dispensed to patients at each visit and will contain a sufficient supply of IFN β -1a (or matching placebo) for each dosing interval. Treatment kits must be stored in a secure location. Accountability for study treatment is the responsibility of the Investigator. More details concerning this responsibility are included in [Section 9.5.5](#).

9.5.4. Blinding of Study Medication

In Parts A and B, a “Dual Assessor” approach (described in [Section 9.1.2.2](#)) will be used to evaluate efficacy and safety.

Details unique to Parts A or B are described below.

Part A

Part A is a randomized, double-blind, placebo-controlled study with limited access to the randomization code. RPC1063 and placebo capsules will be identical in physical appearance. The treatment each patient will receive will not be disclosed to the Investigator, Evaluator, study center personnel, patient, Sponsor and their representatives. The treatment codes will be held according to an IVRS. Further instructions will be provided in a separate IVRS manual.

Part B

Part B is a randomized, double-blind, double-dummy, active-controlled study. RPC1063 and IFN β -1a and their respective matching placebo capsules/injections will be identical in physical appearance. The treatment each patient will receive will not be disclosed to the Investigator, Evaluator, study center personnel, patient, Sponsor and their representatives. The treatment codes will be held according to an IVRS. Further instructions will be provided in a separate IVRS manual.

For details of the emergency procedure for unblinding of individual patients see [Section 9.5.11](#), below.

9.5.5. Study Treatment Storage and Accountability

Study medication should not be used for purposes other than as defined in this protocol.

9.5.5.1. Study Treatment Storage

Part A

RPC1063 and placebo capsules should be stored at room temperature (approximately 25° C, excursions permitted to 15-30°C [59-86°F]) in a dry location. The inactive ingredients used in

the formulations are slightly hygroscopic; therefore, all bottles contain a ½-gram desiccant canister and should be kept tightly sealed when drug product is not being dispensed.

Part B

IFN β-1a prefilled syringes (and matching placebo) must be stored in a secure location. They must be stored at 2-8°C.

RPC1063 capsules will be stored as described for study medication capsules in Part A.

9.5.5.2. Study Treatment Accountability

All supplies of study medication and placebo will be accounted for in accordance with GCP. There will be an individual study drug accountability record for each patient and the Investigator should maintain accurate records of the disposition of all study medication supplies received during the study. These records should include the amounts and dates clinical drug supplies were received, dispensed to the patient, returned by the patient and returned to the Sponsor. If errors or damages in the clinical drug supply shipments occur, the Investigator should contact and the Study Monitor immediately. Each Investigator will provide copies of the study medication accountability records for inclusion in the Trial Master File after database lock. The Study Monitor will periodically check the supplies of study medication held by the Investigator or pharmacist to verify accountability of all medication used.

The Investigator will provide the medication only to the identified patients of this study, according to the procedures described in this study protocol. After the end of the study, the Study Monitor will perform final accountability, package, seal, and prepare for shipment. Medication and all medication containers will be returned to and documentation will be returned to the CRO. The CRO will verify that a final report of drug accountability is prepared and maintained in the Investigator's Study Center File.

9.5.6. Dose Adjustments and Dose Escalation

There is no provision for dose adjustments in this study. Patients who cannot tolerate investigational drug must be withdrawn from the study

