Study assessments will include physical examination, vital signs, blood tests and MRI (without and with Gadolinium contrast). Several of the AEs noted in fingolimod clinical studies may be a consequence of SIP1R stimulation and will therefore be closely monitored in the study. These AEs include bradycardia and heart conduction abnormalities (electrocardiogram [ECG] monitoring, Holter monitoring [Part A only], vital signs), pulmonary toxicity (forced expiratory volume at 1 second [FEV₁], forced vital capacity (FVC) measurements, and lung diffusion capacity testing [DLCO] measurements), macular edema (ophthalmic monitoring including optical coherence tomography [OCT]), cutaneous malignancy (dermatological exams) and hepatotoxicity (liver function tests [LFTs]).

Patients who experience a relapse may receive treatment with intravenous (IV) corticosteroids. The following standardized treatment regimen should be used: as warranted, 1.0 g IV methylprednisolone per day for a maximum of 5 consecutive days. A corticosteroid taper is not allowed. Any deviation from the standardized treatment regimen should be discussed in advance with the Medical Monitor. The Investigator should attempt to maintain therapies or treatments for symptoms related to MS (e.g., spasticity, incontinence, pain, fatigue) reasonably constant throughout the study. However, changes may be made if appropriate for a patient's well-being in the clinical judgment of the treating investigator.

All efforts will be made to follow patients who discontinue prematurely from the treatment due to lack of response, AEs, or other reasons, even if alternative treatment is given. These patients will be followed for collection of safety data, including lymphocyte recovery, and for the assessment of their disease status. The Cognitive Function subscale of the MSQOL-54 will be assessed to evaluate quality of life and subjective cognitive impairment.

STUDY POPULATION AND MAIN CRITERIA FOR INCLUSION/EXCLUSION:

Inclusion Criteria:

1. MS, as diagnosed by the revised 2010 McDonald criteria
2. Exhibiting a relapsing clinical course consistent with RMS and history of brain MRI lesions consistent with MS
3. Ages 18-55 years, inclusive
4. EDSS score between 0 and 5.0 at baseline
5. Meet one of the following disease activity criteria:
 - a. At least 1 documented relapse within the last 12 months prior to screening
 - OR

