Part B is a randomized, double-blind, double-dummy comparison of RPC1063 to IFN β -1a in patients with RMS, per revised 2010 McDonald criteria ([McDonald, 2010](#); [Polman, 2011](#)). Part B will commence after the DMC reviews the Part A interim analysis data and performs a thorough safety review. Patients dosed in Part A will be ineligible for participation in Part B.

Approximately 1200 patients who meet eligibility criteria as assessed during the 30-day screening period will be randomly assigned 1:1:1 to receive one of the three following regimens for 24 months:

- IFN β -1a 30 μ g intramuscular (IM) weekly
- 0.5 mg RPC1063 oral capsule daily
- 1 mg RPC1063 oral capsule daily

The randomization will be stratified by baseline EDSS (≤ 3.5 , > 3.5) and country.

A “dual assessor” approach will be used to evaluate efficacy and safety to prevent potential unblinding as result of observed efficacy, AEs, or laboratory changes (refer to [Section 9.1.2.1](#) for additional details). The treating investigator will evaluate patients every 3 months throughout the study and, if necessary, at unscheduled visits for relapses occurring between scheduled visits.

The blinded evaluator will assess the EDSS. Blinded study coordinators or EDSS evaluators will perform the MSFC and LCLA assessments. The Cognitive Function subscale of the

[figure not shown]
MSQOL-54 will also be assessed to evaluate subjective cognitive impairment. The Paced Auditory Serial Addition Test (PASAT-3) of the MSFC will also be used to evaluate cognitive function.

All efforts will be made to follow patients who discontinue from the treatment due to lack of response, AEs, or other reasons, even if alternative treatment is given. These patients will be followed for collection of safety data, including lymphocyte recovery, and for the assessment of their disease status.

CELGENE PROPRIETARY INFORMATION

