12.1. Adverse Events (AEs)

The AE definitions and reporting procedures provided in this protocol comply with current CFR 21 Part 312. An AE is any untoward medical occurrence that does not necessarily have a causal relationship with the investigational medicinal product. An AE can therefore be any unfavorable or unintended sign, including an abnormal laboratory finding, symptom or disease temporally associated with the use of an investigational medicinal product whether or not considered related to the investigational medicinal product.

Relapses and MS disease progression will be monitored as study endpoints, but will not be recorded as AEs.

AEs will be monitored throughout the entire study. Investigators will ask the patient at each visit if they have experienced any untoward occurrence since the last study visit. All AEs will be recorded on the eCRFs provided: a description of the event, severity, time of occurrence, duration, any action (e.g. treatment and follow up tests) and the outcome should be provided along with the Investigator's assessment of the relationship to the study treatment.

AEs will be recorded from the start of study drug treatment until 28 days following the last dose of treatment with the study drug.

If known, the event diagnosis should be recorded rather than listing individual signs or symptoms. AEs must be graded as being mild, moderate or severe and their approximate duration given. Definitions of severity are as follows:

Mild: an AE usually transient in nature and generally not interfering with normal activities;

Moderate: an AE that is sufficiently discomforting to interfere with normal activities;

Severe: an AE that is incapacitating and prevents normal activities.

Even if the Investigator feels there is no relationship to the study drug, all AEs MUST be recorded in the eCRF. The Investigator is requested to assess the relationship of any AEs to treatment using the following definitions:

Unrelated: those AEs which are clearly and incontrovertibly due to extraneous causes (concurrent drugs, environment etc.) and do not meet the criteria for drug relationship listed under Unlikely, Possible, Probable or Related.

Unlikely: an AE may be considered unlikely if it includes at least the first two features:

- It does not follow a reasonable temporal sequence from administration of the drug.

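### Section 9.5.6 takes intolerant patients out of the study, contradicting the sections that keep patients in follow-up after they stop drug; the wording must be reconciled

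*Protocol*

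**What the plan says.** Section 9.5.6, on dose adjustments, first says that doses cannot be adjusted and then adds: "Patients who cannot tolerate investigational drug must be withdrawn from the study".

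Four other places treat stopping drug and leaving the study as different events:

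- **Synopsis (text common to Parts A and B):** "All efforts will be made to follow patients who discontinue prematurely from the treatment due to lack of response, AEs, or other reasons". This includes patients who move to another therapy, and the purpose is safety data, lymphocyte recovery and disease status.
- **Section 9.1 (Part B):** the same commitment, "All efforts will be made to follow patients who discontinue from the treatment due to lack of response, AEs, or other reasons".
- **Section 9.4.4.1:** "All patients who discontinue study medication should complete an Early Termination Visit". Unless consent is withdrawn or the patient is lost, "they will be asked to undergo a follow-up visit 4 weeks after the last dose for the collection of safety data including lymphocyte recovery", and also to assess disease status.
- **Section 9.4.4.2:** "Patients must be withdrawn from the study for any one of the following reasons". Two reasons follow: loss to follow-up and withdrawal of consent. Intolerance is not one of them.

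Section 12.1 sets the adverse event window: "AEs will be recorded from the start of study drug treatment until 28 days following the last dose of treatment with the study drug". Sections 9.1.2.5 and 12.4 go further for abnormalities of special interest. In general these are followed to resolution or until no more improvement is expected, judged over at least 3 months. Macular edema requires monthly review.

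**The concern.** The protocol gives two answers to the same question: does a patient who cannot tolerate the drug stay in the study? No order of precedence is stated, so sites may differ.

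The patients affected are those whose later course matters for safety. Section 9.4.4.1 lists confirmed liver enzyme elevation, macular edema and marked loss of lung function as grounds for stopping drug. These are the events for which Section 12.4 asks for prolonged follow-up. A site that follows 9.5.6 to the letter could close such a patient's participation before that follow-up is complete, and could end the disease-status follow-up promised in the Synopsis and Section 9.1.

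The planned reporting also blurs the distinction. Section 6 of the Part A SAP counts adverse event as a reason for discontinuing the study, which Section 9.4.4.2 does not.

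**Working it through.** **1. The sections side by side, for a patient who stops because of intolerance**

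| Source | Status after stopping drug | What is still collected |
|---|---|---|
| 9.5.6 | Out of the study | Nothing stated |
| 9.4.4.1 | Off drug | Early Termination Visit; 4-week visit |
| 9.4.4.2 | Not a listed reason for withdrawal | – |
| Synopsis, 9.1 | Followed | Safety and disease status, no visit schedule |
| 9.1.2.5, 12.4 | Followed if an abnormality of special interest occurred | At least 3 months if unresolved |
| 12.1 | – | Adverse events to 28 days after last dose |

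The list in 9.4.4.1 is expressly open-ended; the list in 9.4.4.2 is not. An intolerant patient has also discontinued medication, so 9.4.4.1 applies whatever 9.5.6 says.

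**2. What a literal reading of 9.5.6 removes**

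- *Kept:* the Early Termination Visit, which includes EDSS and MRI (Section 10.5), and the 4-week visit, which includes the differential white cell count (Section 10.6). Lymphocyte recovery at 4 weeks is therefore still measured.
- *At risk:* follow-up after that. Table 3 equates Month 3 with Week 13. For an abnormality found at about the last dose and not yet resolved, the minimum of 3 months runs at least 13 − 4 = 9 weeks past the 4-week visit. The open-ended disease-status follow-up is also at risk.

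**3. Is power at stake?** The plan's own Part B figure first. Inputs from Section 13.2: rates 0.30 and 0.19, dispersion 1.3, 2 years, 90% power, alpha 0.025 (taken as two-sided).

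n = (2.2414 + 1.2816)² × 1.3 × [1/(0.30×2) + 1/(0.19×2)] / [ln(0.19/0.30)]² = 332.4, so 333 per arm, as stated. Then 333/0.83 gives 402, against about 400 planned.

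If the 17% who drop out contribute nothing, 400 × 0.83 = 332 per arm and power is 90.0%. If all are followed to Month 24, power is 94.8%. Planned power already allows for the loss, so any harm to the primary analysis would be bias.

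**4. Can the bias be sized?** Suppose, as an upper bound, that all 17% leave at mid-study. Then 0.17 × 400 × 1 year = 68 of 800 person-years per arm (8.5%) are unobserved. The ratio observed on study is 0.19/0.30 = 0.633. The all-patient ratio depends on assumptions that the documents do not supply:

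| Assumption for the unobserved time | All-patient ratio |
|---|---|
| Equal dropout; one off-drug rate g in both arms, (732×0.19 + 68g)/(732×0.30 + 68g), g = 0.30, 0.45, 0.60 | 0.66, 0.68, 0.69 |
| Equal dropout; each arm's rate multiplied by the same factor m | 0.633 |
| Dropout 24% RPC1063, 10% interferon; m = 1.5 to 2 | 0.655 to 0.676 |
| Dropout 10% RPC1063, 24% interferon; m = 1.5 to 2 | 0.612 to 0.594 |

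The last three rows use 0.633 × [1 + 0.5 d₁(m − 1)] / [1 + 0.5 d₀(m − 1)], where d₁ and d₀ are the dropout proportions on RPC1063 and interferon. The ratio can move either way or not at all.

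**5. Does off-drug time enter the analysis?** The Synopsis describes the Part B primary analysis as ARR during active treatment. Section 13.6.4 divides by total days in the study. Under the first reading, off-drug relapses would not count whatever 9.5.6 says.

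**The case against.** The strongest reply is that this is loose wording in a section about dose changes. Section 9.4.4 is the one written for discontinuation, and a site would go there. Section 9.5.9 shows the same looseness: it speaks of withdrawing persistently non-compliant patients from the study, while 9.4.4.1 treats non-compliance as a reason to stop medication. On this view little is lost, since the two visits and 28 days of adverse event recording survive.

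Much of that stands. The loss arises only where 9.5.6 is applied literally, and it is partial. A reader might infer that post-treatment safety data, including lymphocyte recovery, would disappear; Sections 9.4.4.1, 10.6 and 12.1 do not support that.

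The reply does not remove the contradiction. Section 9.5.6 is phrased as an obligation, and the general instruction in Section 12.4 to follow events to resolution is framed as applying during the study. A site that has withdrawn a patient could regard that instruction as spent.

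It is also fair to object that 9.5.6 does not cause the 68 unobserved person-years. Without it, the specified off-drug schedule is still two visits, and the 4-week visit lists neither EDSS nor MRI. The 17% is dropout of any cause, not intolerance. Both objections are correct.

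**Conclusion.** The contradiction is real and worth correcting. At stake is a partial loss of follow-up in patients who stop for toxicity: the special-interest follow-up beyond 4 weeks (at least about 9 further weeks for an unresolved abnormality found at about the last dose) and the disease-status follow-up promised without a schedule. This rests on sites applying 9.5.6 as written.

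A reader might go further and infer that the trial would overstate the benefit of RPC1063. Assigning RPC1063 leavers 0.45 to 0.60 relapses per year in the lost year, while interferon stays at 0.30, gives (732×0.19 + 68g)/800/0.30 = 0.71 to 0.75 against 0.63 observed. The documents do not support this. It counts all dropout as intolerance, raises the rate in one arm only, and uses rates that appear nowhere in the plan. That intolerance differs by arm is plausible, given different side-effect profiles, but no rate by arm is given. With the conflict over off-drug time and no Part B SAP among the documents, neither the size nor the direction of any bias can be set.

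**What to change.** Reword the sentence in Section 9.5.6 so that it refers to discontinuing study medication, and cross-refer to 9.4.4.1 for what follows and to 9.4.4.2 as the only basis for study withdrawal. State that the follow-up already described in the Synopsis and Sections 9.1, 9.1.2.5, 9.4.4.1 and 12.4 continues. This leaves untouched when or why drug is stopped.

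The cost is one sentence in an amendment. It adds no visit or procedure, because it preserves only what the protocol already asks for.

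It would not secure relapse or MRI outcomes to Month 24. That would need off-drug visits beyond the two in 9.4.4.1, and a decision between the Synopsis and Section 13.6.4 on whether off-drug time counts. Both should be considered separately and costed as such.
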